9.8.1 HCV RNA Sample

HCV RNA sample – the following needs to be documented:

- **Quantitative** HCV RNA by PCR test
 - Test name and result **in IU/mL**
 - Lower limit of detection (LLoD) **in IU/mL** and lower limit of quantification (LLoQ) **in IU/mL**
- **Qualitative** HCV RNA by PCR test
 - Test name and result (**positive/negative**)
 - LLoD **in IU/mL**

9.8.2 Concomitant Medication

Concomitant medication - the following will be documented:

- Concomitant medication used from the first dose of ABBVIE REGIMEN until the end of Follow-up period

It should be verified by the treating physician that concomitant medication can be safely administered with the ABBVIE REGIMEN. Some medications may be contraindicated; some may require dose adjustments due to potential for drug-drug interactions (DDIs). The investigator or qualified designee should review the concomitant medication(s) labels and screen concomitant medications at each visit for potential DDIs.

9.9 Variables

9.9.1 Primary Variable

- The percentage of patients achieving SVR12 (undetectable viral load at 12 week after the last actual dose of the ABBVIE 3D REGIMEN)

9.9.2 Secondary Variables

- Baseline characteristics of patients with HCV Gt1b and compensated cirrhosis treated with ABBVIE 3D REGIMEN
- Co-morbidities and concomitant medication
- Serious and non-serious adverse events

9.10 Data Sources

Data for the study will be collected within clinical interview with the patient and source document at the center. Source documents will be original documents, data and records. This may include hospital records, clinical and office charts, laboratory data/information, pharmacy dispensing and other records, recorded data from automated instruments, etc.

9.11 Study Size

60 patients will be included in this descriptive study without any priory sample size calculation. Convenient sampling methods will be used for patients who attended routine outpatient visits, fulfilled the inclusion/exclusion criteria and had signed a patient authorization form to use and disclose personal health information.

9.12 Data Management**9.12.1 Electronic Case Report Forms**

Data for this study will be recorded in English by each participating center via an electronic data capture (EDC) system using a web-based eCRF. Examinations, diagnostic measures, laboratory assessments, findings and observations routinely performed in patients with CHC included in this cohort, will be transcribed by the investigator or designee from the source documents into the eCRF. For each enrolled patient, the investigator or designee will create a new patient file in the eCRF and a unique patient number will be automatically allocated by the system.

A comprehensive data validation program utilizing front-end checks in the eCRF will validate the data. Automated checks for data consistency will be implemented, discrepancies need to be solved by the researcher in the eCRF before the module can be completed.

Follow-up on eCRF data for medical plausibility will be done by AbbVie personnel (or their representatives). Queries will be generated in the eCRF for online resolution at the site. The investigator or an authorized member of the investigator's staff will make any necessary data corrections to the eCRF. All change information, including the date and person performing the corrections, will be available via the audit trail, which is part of the EDC system. The principal investigator of each site will finally review the eCRFs for

completeness and accuracy of available data and provide his or her electronic signature and date to the eCRFs as evidence thereof.

Access to the EDC system will be provided for the duration of the study through a password-protected method of internet access. Such access will be removed from investigator sites at the end of the site's participation in the study. Data from the EDC system will be archived on appropriate data media (e.g. CD-ROM) and provided to the investigator as a durable record of the site's eCRF data.

9.12.2 Assignment of Preferred Terms

AEs will be coded using the Medical Dictionary for Regulatory Activities (MedDRA) and will be tabulated by primary MedDRA system organ class (SOC) and preferred term (PT). For treatments, surgical and medical procedures the international non-proprietary name (INN) Drug Terms and Procedures Dictionary will be used.

9.13 Data Analysis

9.13.1 Analysis Population, Time Windows and Handling of Missing Data

The target population (TP) is defined as all patients who fulfill the inclusion/exclusion criteria. The core population (CP) is defined as all patients of the TP, who have started the treatment combination recommended in the current local label for their disease characteristics. Patients not receiving the treatment recommended in the local label will be summarized in the non-core population (NCP). In addition, the core population with sufficient follow-up data (CPSFU) is defined as all CP patients, who fulfil one of the following criteria:

- (1) evaluable HCV RNA data ≥ 84 days after the last actual dose of the ABBVIE REGIMEN (i.e. data within the SVR12 time window)

- | (2) a HCV RNA value ≥ 50 IU/mL at the last measurement post-baseline (i.e. no virological response achieved at the last measurement on-treatment or post-treatment)
- | (3) HCV RNA < 50 IU/mL at the last measurement post-baseline, but no HCV RNA measurement ≥ 84 days after the last actual dose of the ABBVIE REGIMEN due to reasons related to safety (e.g. dropped out due to AE) or incomplete efficacy information (e.g. virologic failure such as relapse is reported in the eCRF but date and value of the corresponding HCV RNA test is missing). This means only patients who had virological response at their last on-treatment or post-treatment measurement, but had no HCV RNA measurements ≥ 84 days post-treatment for reasons not related to safety or effectiveness (e.g. lost-to-follow-up or patient not willing to perform an additional HCV RNA test ≥ 84 days post-treatment) will be excluded from this analysis.

The Safety Population (SP) is defined as all patients who received at least one dose of the ABBVIE REGIMEN.

In accordance with the non-interventional nature of the study all HCV RNA measurements will be performed at the sole discretion of the physician and all HCV RNA measurements have to be entered into the eCRF. All recorded HCV RNA values will be assigned to appropriate time points (Visit 1, additional on-treatment visits (if any), EoT visit, 30 days safety follow-up visit and SVR 12 follow-up visit). The time windows for the assignments will be specified in the statistical analysis plan (SAP).

No data will be imputed for any effectiveness or safety analyses except for the analyses of the HCV RNA endpoints. When there is no HCV RNA value in a visit time window post-baseline, but prior to EoT, the closest values before and after the window, regardless of the value chosen for the subsequent and preceding window, will be used for the flanking imputation described below. If a patient has a missing HCV RNA value at a post-Visit 1

visit prior to EoT but has undetectable HCV RNA (with LLoD \leq 50 IU/mL) or unquantifiable, but detectable HCV RNA levels (with LLoQ \leq 50 IU/mL) at both the preceding and succeeding measurements, the HCV RNA level will be considered undetectable or unquantifiable, respectively, at this visit for this patient. In addition, if a patient has an unquantifiable HCV RNA level at the preceding measurement and an undetectable HCV RNA level at the succeeding measurement, or vice versa, the HCV RNA level will be imputed as unquantifiable at this visit for this patient. For virological response at EoT a corresponding backward imputation approach will be applied. This means if HCV RNA is missing at EoT, then unquantifiable or undetectable will be assumed for EoT, if the succeeding HCV RNA value is undetectable or unquantifiable. For SVR12 the single last available HCV RNA measurement \geq 84 days post-treatment will be used. Subsequent to this flanking and backward imputation, if the HCV RNA value remains missing at a specific time point, then the patients will be considered as virological failure at this time point (i.e. not undetectable or unquantifiable).

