The core population (CP) is defined as all patients of the target population (TP) (definition see above), who have started the treatment combination recommended in the current local label for their disease characteristics. Patients not receiving the treatment recommended in the local label will be summarized in the non-core population (NCP). In addition, the core population with sufficient follow-up data (CPSFU) is defined as all CP patients, who have (i) evaluable HCV RNA data ≥ 84 days after the last actual dose of the ABBVIE REGIMEN or (ii) a HCV RNA value ≥ 50 IU/mL at the last measurement or (iii) had HCV RNA < 50 IU/mL at the last measurement, but no HCV RNA measurement ≥ 84 days after the last actual dose of the ABBVIE REGIMEN due to reasons related to safety (e.g. dropped out due to adverse event) or incomplete efficacy information (e.g. virologic failure such as relapse is reported in the electronic case report form (eCRF) but date and value of the corresponding HCV RNA test is missing). The safety population (SP) is defined as all patients who received at least one dose of the ABBVIE REGIMEN.

Descriptive and exploratory statistical methods will be used to analyze the data of the study. All baseline and disease characteristics will be summarized for the CP stratified by the CP analysis groups, which are relevant for scheduled treatment and duration (12 weeks). In addition, baseline summaries will be repeated for the SP and TP without stratification into subgroups. Further details of analysis populations and the CP analysis groups will be specified in the statistical analysis plan (SAP).

The primary effectiveness analysis will be performed for CP patients, stratified by the CP analysis groups. Response rates (i.e. SVR12 rate, end of treatment [EoT] response rate, relapse rate,) will be determined for the various CP analysis groups. The relapse rates will be estimated in patients of the CP analysis groups with EoT response and sufficient HCV RNA measurements post treatment. The relapse rates will be estimated in all patients of the CP analysis groups, who have undetectable HCV RNA measurement at EoT visit. For all rates specified above 95%-confidence intervals (CIs) will be determined using the Clopper-Pearson method.

Milestones:

Start of Data Collection: 10-Mar-2017

End of Data Collection: 10-Dec-2017

Final Report of Study Results: 30-Mar-2018

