9.13.5 Secondary Effectiveness Endpoints

The secondary effectiveness endpoints are:

- The percentage of patients with virological response (HCV RNA <50 IU/mL) at EoT
- The percentage of patients with relapse (defined as HCV RNA <50 IU/mL at EoT followed by HCV RNA ≥ 50 IU/mL)
- The percentage of patients with relapse (defined as at least one documented HCV RNA <50 IU/mL followed by HCV RNA ≥ 50 IU/mL during treatment).

- The number and percentage of patients meeting each and any of the following SVR12 non-response categories:
 - Relapse (defined as HCV RNA <50 IU/mL at EoT or at the last on-treatment HCV RNA measurement followed by HCV RNA ≥ 50 IU/mL post-treatment)
 - Missing SVR12 data and/or none of the above criteria

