9.13.6 Statistical Methods for Analysis of Effectiveness Variables

The simple percentage of patients achieving SVR12 will be calculated and an exact two-sided 95% confidence interval (CI) of the percentage will be computed based on the Clopper-Pearson method.

Corresponding methods will be used for other response rates (EoT response rate, relapse rate). The relapse rates will be estimated in patients of the CP analysis groups with EoT response and sufficient HCV RNA measurements post-treatment.

These analyses will be of exploratory nature, data driven, and will be repeatedly performed for various CP Analysis Groups, since not each covariate might be predictive in each patient group. Furthermore, the fact that treatment regimens will differ in the various patient groups has to be taken into account, when selecting the patient groups for each MLR analysis. Backward selection procedures will be applied to generate the final MLR models which consider only covariates in the selection procedure with a p-value <0.25 in the corresponding univariate logistic regression analysis. A p-value <0.05 will be used for the covariates to stay in the model in a backward elimination step. Logistic regression methods will also be used to investigate the impact of treatment adherence on SVR12.

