 - relapse after EoT (HCV RNA value <50 IU/mL or undetectable/negative at EoT or at the last on-treatment HCV RNA measurement followed by HCV RNA \geq 50 IU/mL or positive post-treatment);
 - failure to suppress (each measured on-treatment HCV RNA value \geq 50 IU/mL or positive);
 - premature study drug discontinuation with no on-treatment virologic failure;
 - missing SVR12 data and/or none of the above criteria.

Figure 9.1 illustrates the patient's distribution by SVR12 response/non-response categories.

P16-253 (CITRIN) _ STATISTICAL ANALYSIS PLAN _ FINAL 2.0 _ 16 Mar 2018

[figure not shown]

Figure 9.1 – Patient's distribution by SVR12 response/non-response categories. Frequencies and percentages with 95% confidence intervals will be calculated for each effectiveness outcomes and will be presented according the section 7.1. Also frequency tables will be repeated for patients in subgroup without missing SVR12 data category.

Effectiveness endpoints (SVR12 achieving, virological response at EoT and relapse after EoT) will be analyzed using univariate logistic regression, if applicable. These analyses will be of exploratory nature, data driven, and will be repeatedly performed for various CP analysis groups, since not each covariate might be predictive in each patient group.

The following parameters can be included in the univariate models as explanatory variables (fixed effect or covariate):

- treatment experience (with/without prior treatment for CHC);
- Child Pugh score;
- result of FibroTest;
- history of liver decompensation;
- age;
- gender;
- race;
- BMI;
- laboratory hematology¹:
 - hemoglobin;
 - platelets;
 - prothrombin time;
 - laboratory clinical chemistry:
 - ALT;

¹ Note that all Hematology variables and all Clinical Chemistry should be in the same units. If it is impossible to bring units to the same the smallest units groups will be accepted as missing. If it is impossible to identify the smallest units groups the corresponding covariate will be deleted from the analysis.

P16-253 (CITRIN) _ STATISTICAL ANALYSIS PLAN _ FINAL 2.0 _ 16 Mar 2018

- AST;
- Gamma-GT;
- total bilirubin;
- albumin;
- creatinine clearance;
- alpha-1-fetoprotein.

Additionally, after univariate model analyses all effectiveness endpoints can be analyzed using MLR (if applicable) which consider only covariates in the selection procedure with a p-value <0.25 in the corresponding univariate logistic regression analysis¹.

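### Under the Protocol's backward imputation, patients without an EoT sample enter the relapse denominator according to their later result, which biases relapse downward; the SAP uses another denominator without saying so

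*Protocol*

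**What the plan says.** **Imputation (Protocol 9.13.1).** For response at EoT the rule works backward from the next sample: "if HCV RNA is missing at EoT, then unquantifiable or undetectable will be assumed for EoT, if the succeeding HCV RNA value is undetectable". An unquantifiable next value has the same effect. Whatever is left over is failure: "if the HCV RNA value remains missing at a specific time point, then the patients will be considered as virological failure at this time point".

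**Denominator (Protocol 9.13.6).** "The relapse rates will be estimated in patients of the CP analysis groups with EoT response and sufficient HCV RNA measurements post-treatment". The abstract repeats this and then adds a second version, covering all patients "who have undetectable HCV RNA measurement at EoT visit".

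**Relapse definition.** Protocol 9.13.5 has two that bear on the period after EoT. The endpoint itself is tied to EoT: "The percentage of patients with relapse (defined as HCV RNA <50 IU/mL at EoT followed by HCV RNA ≥ 50 IU/mL". The SVR12 non-response category is wider: "Relapse (defined as HCV RNA <50 IU/mL at EoT or at the last on-treatment HCV RNA measurement followed by HCV RNA ≥ 50 IU/mL post-treatment".

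**SAP.** Section 9 takes the wider form: "relapse after EoT (HCV RNA value <50 IU/mL or undetectable/negative at EoT or at the last on-treatment HCV RNA measurement followed by HCV RNA" at or above 50 IU/mL, or positive, post-treatment. The effectiveness table shells compute every percentage, relapse included, on the N of the whole analysis population. SAP 7.3 on missing data deals only with adverse event dates and has no HCV RNA imputation. SAP 15 nevertheless declares the SAP consistent with the Protocol.

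**The concern.** A relapse rate is conditional: among patients who had responded by the end of treatment, how many became positive again? Entry to the denominator should therefore rest on information that precedes the outcome. Under Protocol 9.13.1 read with 9.13.6, entry for a patient with no EoT sample is decided by the post-treatment sample, which is also the sample that decides relapse.

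The backward rule is sensible for the EoT response rate, since a patient who is negative 12 weeks after treatment was very probably negative at its end. The trouble arises when the same imputed status selects the patients for the relapse rate.

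Relapse between EoT and SVR12 is a stated secondary objective. HCV RNA testing is left to routine practice, so some EoT samples may be missing. Protocol 9.15 warns that missing HCV RNA can lower the SVR rate; it does not mention that here missing data would make relapse look rarer, which favours the regimen.

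**Working it through.** The documents give no expected relapse rate, no expected share of missing EoT samples and no sample size calculation, so there is no plan figure to reproduce.

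**Inputs from the documents:** N = 60 (Protocol 9.11); exact Clopper-Pearson 95% intervals (9.13.6); the imputation and default rules (9.13.1); the responder denominator (9.13.6); the SAP definition and shells.

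**Assumptions:**
- r: true relapse rate among on-treatment responders with follow-up.
- m: share of them with no EoT sample, taken as independent of relapse.
- q: share of relapsers without EoT whose next sample is still negative.
- s: share of relapsers without EoT who have a suppressed on-treatment sample.

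**Step 1. Classification under 9.13.1 and 9.13.6**

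| EoT sample | Next sample | EoT status | Relapse rate |
|---|---|---|---|
| Observed response | Negative | Responder | Denominator |
| Observed response | Positive | Responder | Numerator and denominator |
| Missing | Negative | Imputed responder | Denominator |
| Missing | Positive | Failure | Neither |

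The last two rows differ only in the outcome.

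**Step 2. Expected estimate.** With q = 0 (the next sample is the SVR12 sample), the numerator is r(1 − m) and the denominator is 1 − mr:

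estimate = r(1 − m) / (1 − mr).

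The relative bias is −m(1 − r)/(1 − mr), slightly smaller in size than m. For r = 5%, m = 10%: 0.045/0.995 = 4.52%. For r = 5%, m = 20%: 0.040/0.990 = 4.04%.

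| True r | m = 5% | m = 10% | m = 20% | m = 30% |
|---|---|---|---|---|
| 2% | 1.90% | 1.80% | 1.61% | 1.41% |
| 5% | 4.76% | 4.52% | 4.04% | 3.55% |
| 10% | 9.55% | 9.09% | 8.16% | 7.22% |

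**Step 3. Early post-treatment samples.** A relapser without EoT whose next sample is negative and a later one positive is imputed as a responder and counted as a relapse. In general the estimate is [(1 − m)r + mrq] / [1 − mr(1 − q)]. At r = 5%, m = 20%, q = 0.5 it is 0.045/0.995 = 4.52%; at q = 1 there is no bias. Protocol Table 2 marks post-treatment HCV RNA only at SVR12, so q is probably small.

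**Step 4. Counts (illustration).** 60 patients, 12 without EoT, 4 relapses among the 48 observed and 1 among the 12:
- Protocol rule: 4/59 = 6.8% (1.9 to 16.5).
- Observed EoT only: 4/48 = 8.3% (2.3 to 20.0).
- All 60, relapses counted alike: 5/60 = 8.3% (2.8 to 18.4).

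**Step 5. No relapses.** The point estimate is 0 either way. The upper limit is 1 − 0.025^(1/n): 6.0% for 0/60 after imputation and 7.4% for 0/48 observed. With q = 0 the 12 imputed patients could only have appeared as non-relapsers, so they add apparent precision but no information on relapse.

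**Step 6. SAP tables.** The denominator is N, so imputation changes nothing there. Taking everyone in N as an on-treatment responder with follow-up, the expected percentage is r[(1 − m) + ms]. At r = 5%, m = 20% this is 5.0% if s = 1, 4.5% if s = 0.5 and 4.0% if s = 0. Any loss is in the numerator and affects only relapsers with neither an EoT nor a suppressed on-treatment sample. Such patients can exist, because visits between Visit 1 and EoT are optional (Protocol 9.1).

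**The case against.** **The SAP governs the tables and does not use this denominator.** This stands. A reader might infer that the reported relapse percentages will carry the denominator bias. The documents do not support that: the shells divide by whole-population N, and SAP 9 counts a patient with no EoT sample, a suppressed on-treatment sample and a later positive. It does not close the matter, because the Protocol still specifies a rate among responders, and the SAP claims consistency without saying that this rate or the imputation was dropped.

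**The backward rule is introduced for virological response at EoT only.** This does not help, because EoT response is what 9.13.6 conditions on. The abstract's second denominator speaks of a measurement at EoT and could be read as excluding imputed values. That makes the plan ambiguous rather than sound.

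**The denominator does not gain only non-relapsers, and the estimate is not always pulled down.** Both limits are right. Step 3 shows a route by which a relapser is imputed in, and with no relapses the point estimate is unbiased.

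**The size is small and assumed.** This largely stands. EoT is one of the minimum visits, and patients who stop early are asked to return for it, so m may be low. The cited earlier study had SVR12 in all 60 patients, so relapse may be near zero. The rate is descriptive, with no test or decision attached.

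**Conclusion.** The concern holds for the Protocol. Sections 9.13.1 and 9.13.6 together make entry to the relapse denominator depend on the outcome for patients with no EoT sample. The relative downward bias is up to about m. At an assumed r of 5% and m of 5% to 30%, the absolute shift is roughly 0.2 to 1.5 percentage points; it is less if an early negative precedes the positive, and zero in the point estimate if nobody relapses. In that last case the upper limit is still too low: 6.0% against 7.4% with 12 of 60 missing. The values of r, m, q and s, and the independence of missing EoT from relapse, are assumptions.

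For the SAP the conclusion is narrower: possible under-counting in the numerator, and an undeclared difference from the Protocol in denominator and imputation. This is worth correcting for a stated secondary objective, but it does not touch the primary SVR12 rate.

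**What to change.** In Protocol 9.13.6 and the abstract, and in SAP 9 and its table shells, state one relapse denominator: patients with an observed HCV RNA response, by the plan's own response definition, at EoT or at the last on-treatment measurement, and with at least one post-treatment HCV RNA value. Add that backward-imputed EoT values are used for the EoT response rate only. The shells then need a separate N for the relapse row.

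The starting point is not new: both the Protocol's non-response category and SAP 9 already accept the last on-treatment value. Entry then rests on data that precede the outcome.

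The cost is a sentence or two in each document, a slightly smaller denominator and a slightly wider interval. In the 12-of-60 example the denominator would lie between 48 and 60, depending on how many of the 12 have a suppressed on-treatment sample. One limit remains: a patient suppressed early in treatment, with no later on-treatment sample and a positive post-treatment result, is counted as a relapse although the virus may have returned during treatment. The existing definitions share this limit.
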